# 2. FINAL CONFIGURATION OF RESEARCH PROTOCOL

# 2.1. PURPOSE

The present study was designed to examine whether and to what extent the application of the Awareness Through Movement (ATM) technique of the Feldenkrais method (FM) will reduce pain, improve functionality and will positively affect psychological parameters in patients with chronic neck pain, both as a single intervention (1st arm) and compared to a protocol of biomedical acupuncture combined with stretching (A-S) (2nd arm).

# 2.2. RESEARCH DESIGN

The present study is a single blind randomized controlled clinical trial with an active control element, where the intervention is the ATM technique and the standard treatment given to the control group is the combination of A-S.

# 2.3. RESEARCH HYPOTHESISES

Two main research questions are formulated regarding the effectiveness of ATM versus a standard treatment regimen consisting of acupuncture and stretching, but also the effectiveness of ATM as monotherapy, which will be investigated through appropriate statistical controls. The formal basis of statistical tests is the null hypothesis under which there is no association between the exposure and the outcome (Killeen, 2005). Starting from the assumption of no relationship, statistical tests quantify the probability that the observed relationship was observed by chance, due to the random sampling distribution. When the null hypothesis cannot be rejected then the observed relationship is attributable to chance rather than a true effect of the exposure on the outcome (Banerjee *et al.*, 2009).

Thus, the null hypotheses to be tested are formulated as follows:

- Research question 1: Effectiveness of ATM (intervention group before the intervention vs. the same group after the intervention)
  - Null hypothesis H0A1: The application of ATM does not affect the pain sensitivity assessed by the Pain Pressure Threshold (PPT) measured

with the pressure algometer (Commander Algometer) in patients with chronic neck pain (main hypothesis).

- Null hypothesis H0A2: The application of ATM does not affect the cervical range of motion (ROM) recorded with the Moover threedimensional (3D) Inertial Motion sensor in patients with chronic neck pain (secondary hypothesis).
- Null hypothesis H0A3: The application of ATM does not affect the strength of deep neck flexor muscles as measured by the Chattanooga Stabilizer Pressure Biofeedback in patients with chronic pain in the cervical spine (secondary hypothesis).
- Null hypothesis H0A4: The application of ATM does not affect the respiratory function assessed by the portable spirometer (MIR Spirodoc) in patients with chronic neck pain (secondary hypothesis).
- Null hypothesis H0A5: The application of ATM does not affect the pain in the cervical spine in terms of its intensity and quality, i.e., its sensory, emotional and behavioral dimensions using the McGill Pain Questionnaire-short form (SFMPQ) in patients with chronic neck pain (secondary hypothesis).
- Null hypothesis H0A6: The application of ATM does not affect the functionality recorded with the Neck Disability Index (NDI) in patients with chronic pain in the cervical spine (secondary hypothesis).
- Null hypothesis H0A7: The application of ATM does not affect the anxiety and depression captured by the Hospital Anxiety & Depression Scale (HADS) in patients with chronic neck pain (secondary hypothesis).
- Null hypothesis H0A8: The application of ATM does not affect the kinesiophobia as measured by the Tampa Scale Kinesiophobia (TSK\_GR) in patients with chronic neck pain (secondary hypothesis).
- Null hypothesis H0A9: The application of ATM does not affect the perception of the fear and the effort to avoid pain in relation to physical and work activities assessed by the Fear Avoidance Beliefs

Questionnaire\_Greek version (FABQ\_GR) in patients with chronic neck pain (secondary hypothesis).

- Null hypothesis H0A10: The application of ATM does not affect the degree of pain catastrophizing recorded by the Pain Catastrophizing Scale (PCS) in patients with chronic neck pain (secondary hypothesis).
- Null hypothesis H0A11: The application of ATM does not affect the quality of life as measured by the Short Form 12-item Health Survey (SF-12) in patients with chronic neck pain (secondary hypothesis).
- Research question 2: Effectiveness of ATM versus A-S
  - Null hypothesis H0B1: The effect of applying ATM does not differ in reducing the pain sensitivity (PPT) in patients with chronic neck pain from applying A-S (main hypothesis).
  - Null hypothesis H0B2: The effect of the application of ATM does not differ in the improvement of the cervical ROM in patients with chronic neck pain from the application of A-S (secondary hypothesis).
  - Null hypothesis H0B3: The effect of applying ATM does not differ in improving the strength of deep neck flexor muscles in patients with chronic neck pain than applying A-S (secondary hypothesis).
  - Null hypothesis H0B4: The effect of the application of ATM does not differ in the improvement of the respiratory function in patients with chronic neck pain from the application of A-S (secondary hypothesis).
  - Null hypothesis H0B5: The effect of the application of ATM does not differ in the reduction of pain in terms of its intensity and quality in patients with chronic neck pain from the application of A-S (secondary hypothesis).
  - Null hypothesis H0B6: The effect of the application of ATM does not differ in the improvement of functionality in patients with chronic neck pain from the application of A-S (secondary hypothesis).
  - Null hypothesis H0B7: The effect of the application of ATM does not differ in the reduction of anxiety and depression in patients with chronic

pain in the cervical spine from the application of A-S (secondary hypothesis).

- Null hypothesis H0B8: The effect of the application of ATM does not differ from the application of A-S in reducing kinesiophobia in patients with chronic neck pain (secondary hypothesis).
- Null hypothesis H0B9: The effect of the application of ATM does not differ in the improvement of perception of fear and effort to avoid pain in relation to physical and work activities in patients with chronic neck pain from the application of A-S (secondary hypothesis).
- Null hypothesis H0B10: The effect of the application of ATM does not differ from the application of A-S in reducing pain catastrophizing in patients with chronic neck pain (secondary hypothesis).
- Null hypothesis H0B11: The effect of the application of ATM does not differ in the improvement of quality of life in patients with chronic pain in the cervical spine from the application of A-S (secondary hypothesis).

The alternative hypotheses to be tested are formulated as follows:

- Research question 1: Effectiveness of ATM (intervention group before the intervention vs. the same group after the intervention)
  - Alternative hypothesis H1A1: The application of ATM affects the pain sensitivity assessed by the Pain Pressure Threshold (PPT) measured with the pressure algometer in patients with chronic neck pain (main hypothesis).
  - Alternative hypothesis H1A2: The application of ATM affects the range of motion (ROM) recorded with the Moover three-dimensional (3D) Inertial Motion sensor in patients with chronic neck pain (secondary hypothesis).
  - Alternative hypothesis H1A3: The application of ATM affects deep neck flexor muscles strength as measured by the Chattanooga Stabilizer Pressure Biofeedback in patients with chronic pain in the cervical spine (secondary hypothesis).

- Alternative hypothesis H1A4: The application of ATM affects the respiratory function assessed by the portable spirometer (MIR Spirodoc) in patients with chronic neck pain (secondary hypothesis).
- Alternative hypothesis H1A5: The application of ATM affects the levels of pain in the cervical spine in terms of its intensity and quality, i.e. its sensory, emotional and behavioral dimensions using the McGill Pain Questionnaire-short form (SFMPQ) in patients with chronic neck pain (secondary hypothesis).
- Alternative hypothesis H1A6: The application of ATM affects the improvement of functionality recorded with the Neck Disability Index (NDI) in patients with chronic pain in the cervical spine (secondary hypothesis).
- Alternative hypothesis H1A7: The application of ATM affects the anxiety and depression captured by the Hospital Anxiety & Depression Scale (HADS) in patients with chronic neck pain (secondary hypothesis).
- Alternative hypothesis H1A8: The application of ATM affects kinesiophobia as measured by the Tampa Scale Kinesiophobia (TSK\_GR) (secondary hypothesis).
- Alternative hypothesis H1A9: The application of ATM affects the perception of fear and the effort to avoid pain in relation to physical and work activities recorded with the Fear Avoidance Beliefs Questionnaire\_Greek version (FABQ\_GR) in patients with chronic neck pain (secondary hypothesis).
- Alternative hypothesis H1A10: The application of ATM affects the pain catastrophizing assessed by the Pain Catastrophizing Scale (PCS) in patients with chronic neck pain (secondary hypothesis).
- Alternative hypothesis H1A11: The application of ATM affects the quality of life captured by the Short Form 12-item Health Survey (SF12) in patients with chronic neck pain (secondary hypothesis).

- Research question 2: Effectiveness of ATM versus A-S
  - Alternative hypothesis H1B1: The effect of applying ATM differs in reducing the pain sensitivity (PPT) in patients with chronic neck pain from applying A-S (main hypothesis).
  - Alternative hypothesis H1B2: The effect of the application of ATM differs in the improvement of ROM in patients with chronic pain in the cervical spine from the application of A-S (secondary hypothesis).
  - Alternative hypothesis H1B3: The effect of applying ATM differs in improving the strength of deep neck flexor muscles in patients with chronic neck pain from applying A-S (secondary hypothesis).
  - Alternative hypothesis H1B4: The effect of applying ATM differs in improving the respiratory function in patients with chronic neck pain from applying A-S (secondary hypothesis).
  - Alternative hypothesis H1B5: The effect of the application of ATM differs in the reduction of pain in terms of its intensity and quality in patients with chronic neck pain from the application of A-S (secondary hypothesis).
  - Alternative hypothesis H1B6: The effect of the application of ATM differs in the improvement of functionality in patients with chronic neck pain from the application of A-S (secondary hypothesis).
  - Alternative hypothesis H1B7: The effect of the application of ATM differs in the reduction of anxiety and depression in patients with chronic pain in the cervical spine from the application of A-S (secondary hypothesis).
  - Alternative hypothesis H1B8: The effect of applying ATM differs in reducing kinesiophobia in patients with chronic neck pain from applying A-S (secondary hypothesis).
  - Alternative hypothesis H1B9: The effect of the application of ATM differs in the reduction of the perception of fear and effort to avoid pain in relation to physical and work activities in patients with chronic neck pain from the application of A-S (secondary hypothesis).

- Alternative hypothesis H1B10: The effect of applying ATM differs in improving pain catastrophizing in patients with chronic neck pain from applying A-S (secondary hypothesis).
- Alternative hypothesis H1B11: The effect of the application of ATM differs in the improvement of the quality of life in patients with chronic pain in the cervical spine from the application of A-S (secondary hypothesis).

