# 2.9. STATISTICAL ANALYSIS

Quantitative variables will be expressed as mean and standard deviation (SD). Qualitative variables will be expressed as absolute (N) and relative (%) frequencies. Pearson's  $\chi^2$  test and Fisher's exact test (where it is necessary) will be used to compare proportions, as well as McNemar test will be used to compare the percentages of kinesiophobia between measurements. Student's t-test or nonparametric criterion Mann-Whitney will be used for the comparison of the quantitative variables between the two groups. The change in the used scales and other indicators of the participants over time will be tested using linear mixed models from which dependence coefficients ( $\beta$ ) and their Standard Errors (SE) will be obtained. The group, the measurement (endline vs baseline) and their interaction term (to be tested in which extent the change is different between measurements in the two groups), will be introduced as independent variables. In the cases, where the interaction term will be found significant, sex, age, BMI and the symptoms duration will be introduced in the model (the chosen confounding factors are the most significant), in order to be tested if the interaction remain significant. Moreover, in the case that measurements at some outcome measures will be found to differ significantly at the initial measurement between the two groups, a result not due to systematic error but found to be due to random sampling. In these cases, their initial values will be entered into the mixed linear models as an independent variable to ensure that the findings from the models are not due to the initial differences between the groups. In cases that will be found significant differences between baseline measurements, between the two groups, the initial measurements will be introduced in linear mixed models as independent variable, in order to be ensured that the findings from these models are not due to initial differences between the groups. All reported p values will be two-tailed and statistical significance will be set at p < 0.05. Analyses will be conducted using the IBM SPSS Statistics 26.0.

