# 2.10. RESULTS

Through the research, the effectiveness or the ineffectiveness of the FM will be highlighted and comparisons will be made between the effect of FM and A-S, regarding specific parameters (outcome measures), that will be evaluated at specific times (before and after the completion of the intervention - five weeks). Findings will be drawn for each hypothesis of both research questions with the aim of verifying or rejecting them. In detail, pain sensitivity, cervical ROM, endurance of the deep neck flexor muscles, respiratory function, intensity and quality of pain, functionality and psychological factors will be assessed and contrasted between the two interventions. After comparing the mean values of the groups in each assessment for each outcome measure, it will be established on the first level if the method under consideration has benefits in patients with chronic neck pain. On the second level, it will be established if it shows statistically significant results compared to the A-S intervention, if non-significant differences are detected between the two groups or if the active control group predominates. The findings will be presented for each outcome measure separately.

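### Section 2.3 treats a non-significant result as chance rather than a true effect, and nothing later stops an inconclusive ATM versus A-S comparison being read as no true difference

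*Combined protocol and SAP*

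**What the plan says.** Section 2.3 opens with a short account of hypothesis testing that ends: "When the null hypothesis cannot be rejected then the observed relationship is attributable to chance rather than a true effect". The list of null hypotheses follows directly, 11 for each of the two research questions. The main between-group null, H0B1, is that the effect of ATM "does not differ in reducing the pain sensitivity (PPT) in patients with chronic neck pain from applying A-S (main hypothesis"). Its alternative is two-sided: "The effect of applying ATM differs in reducing the pain sensitivity (PPT").

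Section 2.9 fits linear mixed models with group, measurement and their interaction. From these, coefficients and "their Standard Errors (SE) will be obtained"; and "statistical significance will be set at p < 0.05", two-tailed.

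Section 2.10 expects the study to show the method to be either effective or ineffective. It adds: "Findings will be drawn for each hypothesis of both research questions with the aim of verifying or rejecting them". For the comparison with A-S it foresees three outcomes: ATM significantly better, or "if non-significant differences are detected between the two groups or if the active control group predominates". Section 2.11 is equally two-way: a verified hypothesis agrees with earlier studies, and one that is not verified contradicts them.

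**The concern.** A p value above 0.05 means that the data do not exclude a zero difference at that level. It does not mean that the difference is zero, or that what was observed is only chance. The sentence in 2.3 says the second thing, and no later section corrects it.

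This matters most for research question 2. ATM is compared with an active treatment and the between-group nulls all state that the two do not differ. If such a null is not rejected, the wording in 2.3, together with the verify-or-reject language in 2.10, gives an author grounds to conclude that ATM and A-S do not truly differ. The trial has no margin and no planned interval with which to support that. Research question 1 has the same weakness: a non-significant change within the ATM group could be written up as ineffectiveness.

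**Working it through.** **Inputs.** Section 2.5.1.1: effect size 0.25, 80% power, 5% significance, two equal groups, 126 subjects, 20% dropout, final number about 152. Section 2.9: two-tailed tests. The documents do not give the pre-post correlation, so it is assumed to lie between 0.3 and 0.8.

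**The plan's own figure.** n per arm = 2(1.96 + 0.842)² / d². With d = 0.5 this is 62.8, so 63 per arm and N = 126, as stated. With d = 0.25, which is what the written formula for the effect size gives, it is 252 per arm and N = 504. So 126 fits only if 0.25 is read as Cohen's f, equal to a difference of 0.5 SD. That inconsistency is a separate issue; both differences are carried below. The final number is 126 × 1.2 = 151.2, rounded up to 152.

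**Unadjusted comparison after dropout.** 152 × 0.8 = 121.6, so about 61 per arm.

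- 95% half-width = t(0.975, 120) × √(2/61) = 1.980 × 0.181 = 0.36 SD.
- Two-group F-test power at N = 122 is 0.278 for 0.25 SD and 0.782 for 0.50 SD. The chance of a non-significant result is therefore 1 − 0.278 = 72% and 1 − 0.782 = 22%. At N = 126 the figures are 71% and 20%.
- Illustration: an observed difference of 0.20 SD would have an interval of 0.20 ± 0.36, or −0.16 to 0.56 SD. It is non-significant, yet compatible with a difference above 0.5 SD.

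**Planned comparison.** With two measurements and complete data, the group-by-measurement interaction is the difference between groups in mean change. Assuming equal SDs at both times, the SD of change is √(2(1 − r)) in baseline-SD units. At N = 126 the half-width is t(0.975, 124) × SD of change × √(4/126). Power uses the normal approximation.

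| Assumed r | SD of change | 95% half-width (baseline SD) | Non-significant at 0.25 SD | Non-significant at 0.50 SD |
|---|---|---|---|---|
| 0.3 | 1.183 | 0.42 | 78% | 34% |
| 0.5 | 1.000 | 0.35 | 71% | 20% |
| 0.7 | 0.775 | 0.27 | 56% | 5% |
| 0.8 | 0.632 | 0.22 | 40% | 1% |

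**Could the trial support a claim that the treatments are alike?** The plan gives no margin. For assumed margins of 0.25, 0.3, 0.4 and 0.5 SD of the analysed quantity and no true difference, two one-sided 5% tests at N = 126 have power of about 0%, 3%, 45% and 76%.

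**The case against.** The sentence closes a general, referenced introduction to hypothesis testing. The operative criterion is in 2.9, which sets the significance level and does not repeat the wording. Calling the sentence the formal decision rule for all 22 nulls would go too far.

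A reader might also infer that the plan commits to reporting a null comparison as no difference, or as equivalence. The documents do not support that. Section 2.10 names the category as a non-significant difference, which is a correct description, and no section claims equivalence or non-inferiority. The verify-or-reject sentence is ambiguous too, because it could refer to the alternatives, which are also listed in full. Nor do the documents show that a non-significant H0B1 is likely; the presence of an active comparator does not establish it.

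The coefficient and its standard error already determine an interval, roughly the estimate ± 2 SE, so the information would exist. The percentages above measure power, which a change of wording would not alter.

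All of this stands, and it limits the point to what the plan permits. It does not remove the point. The sentence is wrong as written and uncorrected, 2.10 and 2.11 leave no place for an inconclusive result, and no section asks for the interval or bases a conclusion on it.

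**Conclusion.** The inference in 2.3 is invalid and should be corrected. Followed as written, the plan allows an inconclusive ATM versus A-S result to be read as no true difference, and nothing in it prevents this. The documents do not go as far as saying that it will be so reported.

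The exposure depends on the true difference and on the analysis, so no single percentage describes this trial. The 72% and 22% belong to an unadjusted comparison. For the planned interaction, the range at 0.25 SD stays substantial across the assumed correlations, while at 0.50 SD it becomes negligible when the correlation is high. The wording is wrong under either reading of the 0.25 effect size.

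**What to change.** 1. In 2.3, replace the sentence with one to this effect: *a non-significant result is inconclusive and will not be taken as evidence of no effect or of equivalence.*
2. In 2.9 and 2.10, require the ATM minus A-S difference in change (the group-by-measurement interaction) with its 95% confidence interval for every outcome.
3. In 2.10 and 2.11, word the conclusions from that interval, and add an inconclusive category beside those for ATM better and A-S better.

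This costs a few sentences. The interval follows from the coefficient and standard error already planned. No new data, patients or margin are needed unless the sponsor wishes to claim equivalence or non-inferiority, in which case a margin would have to be justified and fixed in advance.

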# 2.4. OBJECTIVE GOALS

Objectives of the study are summarized in the investigation of statistically significant differences in the outcomes of interest, i.e. in the measurements for pain sensitivity, intensity and quality (pressure algometer and SFMPQ), functionality (NDI), ROM (Moover 3D Inertial Motion sensor), endurance of deep neck flexor muscles (Chattanooga Stabilizer Pressure Biofeedback), respiratory function (portable spirometer) and psychological parameters (HADS, TSK, FABQ, PCS, SF-12). Differences in the outcomes of interest may arise:

a) between the start time (baseline) and the end time of the study within the A-ATM group (A-ATM group at baseline versus A-ATM group after the intervention).

b) between the compared groups of the clinical trial {group A ATM (Intervention Group) versus group B A-S (Active Control Group)}, both at the beginning of the study, as well as after the intervention.

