# 2.5. MATERIAL AND METHOD

## 2.5.1. SAMPLE

## 2.5.1.1. SAMPLE CHARACTERISTICS

During the initial calculation of the sample number, the number of the participants was determined, with purpose, the method of Analysis of Variance (ANOVA) in two groups of equal population, to identify a standardized effect size equal to 0.25 with a power of 80% and a level of statistical significance of 5%. The standardized effect size is defined as follows: Let the measurement tool X and groups A, B and  $\mu$ A,  $\mu$ B

be the mean values of X in groups A and B. SD is the Standard Deviation of X in the whole population. The effect size is given by the formula  $(|\mu A-\mu B|)/SD$ . The calculation was performed with the program G\*power version 3.1.9.7\* and the necessary sample size was calculated at 126 subjects. According to the relevant literature, similar standardized sample sizes have been used in two studies dealing with chronic neck pain (Lundblad *et al.*, 1999; Malmgren-Olsson *et al.*, 2009). Moreover, a dropout rate of 20% was expected, so a final number of around 152 patients is realistic for this study.

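### Section 2.4(b) makes a chance baseline difference between arms an objective, and 2.9 lets its p-value choose the model; one baseline-adjusted model should be fixed in advance for every outcome

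*Combined protocol and SAP*

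**What the plan says.** Section 2.4 frames the objectives as the "investigation of statistically significant differences in the outcomes of interest". Item (b) covers ATM against A-S "both at the beginning of the study, as well as after the intervention". Item (a), separately, is the before-after comparison within the ATM arm.

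Section 2.9 specifies a mixed model with group, measurement (endline versus baseline) and their interaction. It then adds a conditional rule, stated twice: "In cases that will be found significant differences between baseline measurements, between the two groups", the baseline value is added as an independent variable. The same paragraph attributes such a difference to random sampling, not systematic error. It also plans t-tests or Mann-Whitney tests between the arms without naming the time point. On the error level it says: "All reported p values will be two-tailed and statistical significance will be set at p < 0.05". No multiplicity adjustment is stated.

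Section 2.5.1.2 describes simple 1:1 randomisation with 76 patients per arm. None of the null hypotheses in 2.3 (11 per research question) concerns a difference between arms at baseline.

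**The concern.** After random allocation the two arms are samples from one population at baseline, so a significant baseline difference is a chance event and says nothing about ATM. Listing it as an objective invites a result that no hypothesis asks for.

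The more practical problem is the trigger. Whether a baseline imbalance distorts the treatment comparison depends on its size and on the correlation of baseline with endline, not on whether its p-value falls below 0.05. A rule based on the p-value gives different outcomes different models, chosen after the data are seen. It also leaves imbalances just short of significance to an analysis that handles them poorly. This matters most for PPT, the primary outcome.

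**Working it through.** **Inputs.** From the documents: 76 per arm (2.5.1.2), two-sided 5% (2.9), two measurements per patient (2.9, 2.10). Assumed, because the documents do not give them: pre/post correlation ρ of 0.3, 0.5 and 0.7, equal SD at both visits, and correlation between outcome scores of 0 to 0.5.

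**The plan's own figures.** 126 × 1.2 = 151.2, which gives 152, or 76 per arm. The plan gives no error rate for the baseline tests or the switch.

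**1. When the trigger fires.** The standard error of a difference in means, in SD units, is √(2/76) = 0.1622. With t(0.975, 150) = 1.976, the trigger is 1.976 × 0.1622 = 0.32 SD.

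**2. What happens just below it.** Take a chance imbalance of 0.30 SD and no treatment effect.

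- Interaction (a comparison of changes): mean −(1−ρ) × 0.30; critical value 1.976 × √(2(1−ρ)) × 0.1622.
- Endline-only test: mean ρ × 0.30; critical value 0.32.
- Both have conditional SD √(1−ρ²) × 0.1622.

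| ρ | Conditional SD | Interaction bias | Critical value | Type I error | Endline-only bias | Critical value | Type I error |
|---|---|---|---|---|---|---|---|
| 0.3 | 0.155 | −0.21 | 0.379 | 13.7% | +0.09 | 0.321 | 7.2% |
| 0.5 | 0.140 | −0.15 | 0.321 | 11.3% | +0.15 | 0.321 | 11.3% |
| 0.7 | 0.116 | −0.09 | 0.248 | 8.8% | +0.21 | 0.321 | 17.0% |

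The signs differ. The interaction subtracts the whole imbalance although part of it would have regressed to the mean; the endline-only test subtracts nothing.

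**3. How often, and on average.** With a normal imbalance of SD 0.1622, a value between 0.30 SD and the trigger occurs for 1.6% of outcomes. Averaging the conditional error over all imbalances below the trigger gives, for ρ = 0.3, 0.5 and 0.7, 3.8%, 4.1% and 4.4% for the interaction and 4.6%, 4.1% and 3.4% for the endline-only test.

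**4. What always adjusting does.** In 20,000 simulated null trials per correlation, those with a baseline z between 1.5 and 1.96 in absolute value gave:

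- interaction: bias −0.08 to −0.19 SD, error 0.07–0.12;
- endline-only test: bias +0.09 to +0.19 SD, error 0.07–0.13;
- ANCOVA: bias about 0.00, error 0.048–0.056.

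ANCOVA is also more precise. The variance of the change-score comparison relative to it is 2(1−ρ)/(1−ρ²) = 2/(1+ρ), that is 1.54, 1.33 and 1.18.

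**5. When the trigger fires.** In the model of 2.9 the baseline value is itself an outcome row. A baseline covariate entered as a main effect takes the same value in both rows of a patient, so it cancels from the change. With complete data the interaction therefore stays the difference in mean changes. In two simulated data sets the estimate was −0.294 with and without the covariate (ANCOVA −0.088), and −0.099 with and without it (ANCOVA +0.033). Only the standard error moved.

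**6. Chance of at least one significant baseline difference.** Under independence it is 1 − 0.95^k:

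- 11 domains: 43%, with 0.05 × 11 = 0.55 expected;
- 27 scores: 75%, with 1.35 expected;
- 30 scores: 79%, with 1.5 expected.

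At a between-score correlation of 0.3 to 0.5 the figure for 27–30 scores falls to roughly 50–65%. The 27 and 30 are counts made from the outcome sections (PPT sites, ROM, flexor test, spirometry, questionnaire scores); the plan lists no such number.

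**The case against.** The strongest reply is that the plan already treats these differences as chance. Section 2.9 says so, 2.3 has no baseline hypothesis, and 2.10 promises findings per hypothesis. On that view 2.4(b) is loose drafting. This stands to a large extent: a reader might infer that baseline differences will be presented as effects of ATM, and the documents do not support that. The wording of 2.4(b) still needs to be brought into line with 2.3 and 2.9.

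Second, a reader might infer that false baseline differences are nearly certain. The figures above do not support this; likely, if all scores are tested, is as far as they go.

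Third, it may be said that imbalances below the trigger go uncorrected and inflate the error rate. Neither half holds for the main model. The interaction removes the imbalance and overshoots; full non-correction applies only to an endline-only test. The error averaged over non-triggering imbalances is below 5%, and a switch to true ANCOVA would itself have an overall error of 4.1–4.5%. What survives is the conditional bias, the lost precision, and a rule that does not do what it is meant to do.

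Fourth, the phrase in 2.10, "After comparing the mean values of the groups in each assessment for each outcome measure", might be read as drawing a verdict on ATM from a baseline comparison of the arms. That is strained. The first level there can be research question 1, the before-after comparison, which needs the baseline mean.

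**Conclusion.** The concern holds in a limited form. A baseline comparison between arms does not belong among the objectives, and a baseline p-value should not choose the model.

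The harm is conditional: at an imbalance of 0.30 SD, type I error is about 9–14% for the interaction and 7–17% for an endline-only test, with biases of 0.09 to 0.21 SD in opposite directions. Across all non-triggering imbalances the error is 3.4–4.6%, so the 5% level is not threatened overall. When the rule is triggered, it leaves the interaction estimate where it was.

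These figures rest on pre/post correlations of 0.3–0.7, equal variances, 76 analysed per arm and complete two-visit data. Step 5 also assumes that baseline enters as a main effect only, since 2.9 mentions no interaction of baseline with measurement. Calling every baseline difference chance assumes that allocation followed the random sequence; 2.5.1.2 describes how the sequence is generated but not its concealment.

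**What to change.** - **2.4(b):** cut the reference to the start of the study, so that the between-arm objective concerns the post-intervention effect only.
- **2.9, baseline:** present baseline values by arm as mean (SD) or n (%), without significance tests, and delete both statements of the conditional rule.
- **2.9, model:** for every outcome, starting with PPT, estimate the between-arm effect with one model form fixed in advance. This can be ANCOVA of the endline value on group and baseline, or a longitudinal model in which the arms share a common baseline mean. State that the t-test or Mann-Whitney comparison does not replace it.
- **2.10:** keep the reference to each assessment, because research question 1 needs the baseline mean. If the sentence is edited, add only that the between-arm comparison is the baseline-adjusted endline difference.

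The cost is wording in two or three sections. No extra data or patients are needed, fewer tests are run, and precision improves.
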